8.6.2 PGIS and PGIC

Participants will rate their global impression of CIDP symptom severity and fatigue severity respectively, on a 5-point Likert severity scale ranging from “none” to “very severe”.

Participants will rate their global impression of change (if at all) in CIDP symptom and fatigue respectively, on a 7-point Likert severity scale ranging from “very much improved” to “very much worse” from Baseline/start of clinical study treatment to the scheduled visits.

Frequencies of study participants scoring in the respective categories in Patient Global Impressions of Severity (PGIS) and changes in frequencies from Baseline will be presented via a shift table by visit per treatment group and listed by treatment group at each scheduled assessment during the Treatment and Observation Periods.

Patient Global Impressions of Change (PGIC) will be summarized via frequencies of each response by visit and treatment group and listed by treatment group at each scheduled assessment during the Treatment and Observations Periods.

9 PHARMACOKINETICS AND PHARMACODYNAMICS

9.1 Pharmacokinetics

Pharmacokinetic variables of rozanolixizumab like AUC (area under the curve), C_{max} (maximum concentration) cannot be derived, since blood sampling will be performed at 1 time point post-dosing per visit only. Thus, PK is restricted to concentration data.

Concentration data will be summarized for rozanolixizumab by exposure (%) categories and time point using the number of available observations, mean, median, SD, minimum, maximum,

geoMean, (and associated 95% CI), and geoCV% (assuming log-normally distributed data) based on the PK-PPS. Definitions and rules for the exposure (%) categories are provided in Section 10.1.

Concentration data will be summarized for treatment rozanolixizumab by time point and ADA status (6 classifications; see Section 9.3.2) using the number of available observations, mean, median, SD, minimum, maximum, geoMean, (and associated 95% confidence intervals), and geoCV (assuming log-normally distributed data) based on the PK-PPS.

Individual concentrations of rozanolixizumab as well as planned and actual dose administered will be listed by treatment group for the SS and summarized for the PK-PPS, and will include the actual sampling time in days relative to the previous dose.

The following rules will apply for PK data listings and summaries:

- Values below the LLOQ will be reported as BLQ.
- Descriptive statistics of concentrations will be calculated if at most 33% of the individual data points at a timepoint are missing or are not quantifiable (<LLOQ). Values that are BLQ will be replaced by the numerical value of the LLOQ/2 in this instance. However, if $n \leq 3$, then only n, minimum and maximum will be presented as summary statistics. The other descriptive statistics will be left blank. If more than 33% of data points is missing then no summary statistics are given, irrespective of n.
- If no study participants have data, only $n=0$ will be presented. The other descriptive statistics will be left blank.
- The 95% CI lower and 95% CI upper should be left blank if the SD (or equivalently, the geoCV) is 0.
- The geoCV will be calculated using the following formula where SD is the standard deviation from the log-transformed data

$$\text{geoCV (\%)} = \text{sqrt}[(\exp(\text{SD}^2) - 1)] \times 100.$$

For each study participant, individual concentration versus time (week) profiles will be presented graphically in linear and semi-logarithmic scale. In addition, combined individual (spaghetti plots) concentration versus time profiles will be presented in linear and semi-logarithmic scale with all study participants overlaid on the same figure.

All figures will include the LLOQ on the semi-logarithmic plots.

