14.4.2 Pharmacokinetic analyses

Pharmacokinetic variables of rozanolixizumab like AUC (area under the curve from 0 to infinity) and C_{\max} (maximum observed plasma concentration) cannot be derived, due to the sparse blood sampling scheme. Thus, PK is restricted to concentration data.

In contrast to the general descriptive display, concentration data will be summarized by actual dose received and time point using the number of available observations, mean, median, SD, minimum, maximum, geometric mean (and associated 95% CIs), and geometric coefficient of variation (assuming log-normally distributed data). Values below the lower limit of quantification (LLOQ) will be reported with a clear sign indicating that they were below the LLOQ. Descriptive statistics of concentrations will be calculated if at least two-thirds of the individual data points are quantifiable (\geq LLOQ). Individual concentrations of rozanolixizumab will also be displayed graphically.

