14.4.3 Pharmacodynamic analyses

For all PD variables, descriptive statistics for the value, change from Baseline, and/or percentage change from Baseline will be tabulated by actual dose received and time point.

The PD variables will include serum IgG and IgG subclass and NF-L.

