3.6 Treatment assignment and treatment groups

All study participants will receive rozanolixizumab in the OLE.

Analyses will be performed by treatment group and for all study participants where stated. The treatment groups will be displayed as follows in the TFLs:

- Treatment group 1: Newly treated (ie, study participants treated with placebo in parent study)
- Treatment group 2: Previously treated (ie, study participants treated with rozanolixizumab in parent study)

Participants with the reduced dose due to tolerability issues will be mapped under the same treatment groups. These study participants will be flagged in the listings. For the Observation period the same treatment groups will be displayed.

It is expected that study participants will have received treatment as randomized in CIDP01 and hence safety and efficacy analyses will be based on the randomized treatment group in CIDP01. However, if after unblinding of CIDP01 it is determined that a study participant has received

treatment different to the treatment they were randomized to, then for safety analyses the study participant will be allocated according to the actual treatment they received.

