9.2.1 Total Serum IgG

Total Serum IgG concentrations and IgG subclasses will be listed by treatment group and timepoint including absolute changes from Baseline and percentage changes from Baseline. Descriptive summaries (including n, arithmetic mean, median, SD, minimum and maximum) will be presented by treatment group and timepoint and ADA status (6 categories; see Section 9.3.2) for absolute values, changes from Baseline and percentage changes from Baseline.

Study participant total Serum IgG will be plotted against planned time. Mean Serum IgG, mean change from Baseline and percentage change from Baseline will be plotted against planned time by treatment group.

For each study participant, the minimum value and maximum decrease (absolute and percentage) from Baseline in total serum IgG concentration during the study (using all available data up to cut-off point) will be listed. The minimum value and maximum decrease will be summarized by treatment group. If a decrease from Baseline in IgG is not observed in a given study participant, the maximum decrease will be reported as the smallest increase from Baseline.

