10.1 Extent of exposure

The initial dose administered will be based on the dose at the time of completion of the Treatment Period from the parent study (eg, CIDP01). For study participants who had a gap period between the parent study (eg, CIDP01) and CIDP04, a starting dose of [REDACTED] will be used (see protocol Table 7-1).

The intended dose will be calculated based on the study participant's weight at screening (where applicable) or Baseline in CIDP04 for Treatment Period Part 1. For Treatment Period Part 2, body weight is collected every 6 months starting at first visit in this period and the most recent weight will be used to select the correct volume for dose infusion from these timepoints. The calculation is done as follows for the applicable weight:

$$\text{Intended dose (mg)} = \text{weight (kg)} * [REDACTED]$$

The IMP solution contains [REDACTED] of rozanolixizumab. Actual dose in mg at Visit (i) will be calculated as follows:

$$\text{Actual dose at Visit (i) (mg)} = \text{Total actual volume delivered at Visit (i) (mL)} * [REDACTED]$$

where actual volume delivered is collected in eCRF, and in case of interruption it should be calculated as the sum of actual volumes delivered.

Overall exposure (%) will be calculated as mean exposure (%) at each visit as follows:

$$\text{Overall exposure (\%)} = \text{mean}([\text{Actual dose at Visit (i) (mg)} / \text{Randomized dose (mg)} - 1] * 100).$$

Overall exposure will be categorized as follows:

- < -10%
- $\geq -10\%$ and $\leq +10\%$
- $> +10\%$

The exposure categories will be used for the definition of the MFAS as well as the representation of Pharmacokinetic data ([Section 9.1](#)).

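### The SAP replaces the protocol's PK and PD summaries by actual dose received with a study-long mean exposure category for concentrations and no dose split for IgG, and does not record the change

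*SAP*

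**What the plan says.** For PK, Protocol 14.4.2 states that "concentration data will be summarized by actual dose received and time point". For all PD variables, Protocol 14.4.3 states that descriptive statistics "will be tabulated by actual dose received and time point", and it names serum IgG, IgG subclasses and NF-L as the PD variables.

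For PK, SAP 9.1 states: "Concentration data will be summarized for rozanolixizumab by exposure (%) categories and time point using the number of available observations". A second PK summary is by ADA status. The categories come from SAP 10.1: "Overall exposure (%) will be calculated as mean exposure (%) at each visit as follows". The result is cut into three bands: below −10%, −10% to +10% inclusive, and above +10%.

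For IgG, SAP 9.2.1 says that descriptive summaries "will be presented by treatment group and timepoint and ADA status", with no dose or exposure split. SAP 9.2 describes no NF-L table. SAP 3.6 adds: "Participants with the reduced dose due to tolerability issues will be mapped under the same treatment groups"; these participants are flagged in listings.

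SAP Section 1 says that changes from the protocol are documented in 3.9. Section 3.9 lists several, but not this regrouping.

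**The concern.** CIDP04 has two dose tables, Tables 7-1 and 7-2. Protocol 7.2 allows a reduction for tolerability and, in Part 2, for recurrent low IgG. Protocol 6.4.1.2 and 6.4.1.3 allow a restart at the reduced dose in Part 2. Dose is therefore a property of the sample, not of the participant, and one label per participant cannot say which dose lay behind a given concentration.

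The planned PK table may therefore not show concentration at each dose level, and no planned table shows IgG at each dose level. For IgG there is also a selection problem. Those reduced for low IgG are chosen because of the very variable being tabulated, and their later values are pooled with full-dose values in the Part 2 means.

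**Working it through.** **Inputs.** Dosing is weekly: 24 doses in Part 1 and up to 76 with Part 2 (SAP 3.2.1.2). PK samples at dosing visits fall at Visits 2, 4, 8, 14, 18 and 22 (Weeks 1, 3, 7, 13, 17, 21) and at Weeks 25, 37, 49 and 61 (Protocol Table 5-1 and Table 11-1). From Visit 14 on they are predose only. Dose values are redacted, so the ratio r of reduced to full dose is an assumption, shown from 0.5 to 0.9. The plan states no figure of its own to reproduce.

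**Reference dose.** The SAP 10.1 formula divides actual dose by a randomized dose, but CIDP04 has no randomization and the section defines an intended dose. Two readings are possible.

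*Reading A: the reference stays at the full dose.* If k of N doses are reduced and the rest equal the reference:

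overall exposure (%) = −(1 − r) × (k/N) × 100

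The below −10% band requires k > 0.10 × N/(1 − r).

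| r | N = 76: limit | fewest k | reduction by | N = 24: fewest k |
|---|---|---|---|---|
| 0.5 | 15.2 | 16 | Week 61 | 5 |
| 0.7 | 25.3 | 26 | Week 51 | 9 |
| 0.8 | 38.0 | 39 | Week 38 | 13 |
| 0.9 | 76.0 | never | – | never |

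Consequences at r = 0.7:

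- 76 doses, reduced from Week 51: k = 26, exposure −0.3 × 26/76 = −10.3%. All nine earlier PK visits (Weeks 1, 3, 7, 13, 17, 21, 25, 37, 49) go to the below −10% band although no reduced dose had been given. In newly treated participants the Week 1 predose sample follows no rozanolixizumab at all.
- 76 doses, reduced from Week 52: k = 25, exposure −9.9%. Reduced from Week 60: k = 17, exposure −6.7%. In this range the participant stays in the middle band, and the Week 61 trough, which follows a reduced Week 60 dose, is summarized with full-dose samples. A first reduction at Week 61 itself does not have this effect, because that trough follows a full Week 60 dose.
- 24 doses, reduced from Week 17: k = 8, exposure −0.3 × 8/24 = −10.0%, which the inclusive limit keeps in the middle band. The Week 21 predose sample, taken after reduced doses, sits with full-dose samples.

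*Reading B: the reference is the currently assigned dose.* A participant who receives the assigned dose has an exposure near 0% at either level. Both levels then fall in the middle band.

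Under neither reading does the category identify the dose behind a sample, so settling the denominator alone does not cure this. For IgG there is no category at all.

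**The case against.** The strongest reply is that the exposure categories implement the protocol's wording. The rationale for Amendment 2 (Protocol 18.4) links the actual-dose wording to the ±10% allowance around target, and the SAP bands are cut at ±10%. The protocol does not define actual dose received as a choice between Table 7-1 and Table 7-2. This explains where the bands came from and makes them a coarse dose measure for PK. It does not make them equivalent: the protocol asks for dose by time point, and a mean over all visits attaches later doses to earlier samples. For IgG the reply has nothing to offer.

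A reader might infer that concentration and IgG cannot be tied to dose at all. The documents do not support that. SAP 9.1 lists each concentration with planned and actual dose and days since the previous dose, SAP Section 7 lists the volume delivered, and SAP 3.6 flags reduced-dose participants. Nor is IgG recovery on the lower dose wholly hidden: SAP 9.2.1 lists IgG with changes from Baseline and plots each participant's total IgG. But the IgG listing names no dose column, and the flag is worded for tolerability reductions only.

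A reader might also infer that the PK table necessarily misfiles full-dose samples. That holds only under Reading A and for some ratios and timings.

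SAP Section 1 keeps the protocol's analysis unless otherwise specified, so the by-dose tables might be thought to survive. But the same section says that the SAP defines the tables for the CSR, and 9.1 and 9.2.1 specify other groupings.

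Two cautions about a remedy stand. Protocol Section 2 gives IgG a half-life of about 3 weeks, so a value soon after a reduction still reflects earlier dosing. And a by-dose IgG table compares selected groups.

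**Conclusion.** The concern holds as an undeclared departure from Protocol 14.4.2 and 14.4.3: the PK and IgG summary tables can mix dose levels, and dose can be traced only through listings. The departure and its absence from SAP 3.9 rest on the text alone. The misfiling counts are illustrations. They assume a full-dose reference, an assumed r, all 76 doses given (Part 2 is optional and may be shortened), a single lasting reduction, and full doses exactly equal to the reference with weight-band rounding ignored. How many participants will be reduced is unknown. PK and PD are exploratory objectives and the tables are descriptive, so the primary safety analysis is unaffected. The change should be made, but the study does not depend on it.

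**What to change.** 1. In SAP 9.1, summarize concentration by the dose level (Table 7-1 or Table 7-2) received at the rozanolixizumab infusion preceding each sample, by time point. Show predose samples taken before any rozanolixizumab as pre-treatment.
2. In SAP 9.2, add the protocol's by-dose, by-time-point summary for total IgG, IgG subclasses and NF-L, and keep the treatment-group tables. Label it descriptive, show time since dose reduction, and note that participants reduced for low IgG are a selected group.
3. Flag every dose reduction in listings, whatever its reason.
4. Keep the overall exposure categories for the MFAS, and record in SAP 3.9 any departure that remains.

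The cost is SAP wording and one derived variable from infusion records already in the eCRF. The downside is small reduced-dose cells. For PK, SAP 9.1 shows only n, minimum and maximum when n ≤ 3. For PD, SAP 3.1 does so when n < 3 and adds mean and median at n = 3.

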2.1.3 Exploratory objectives

The exploratory objectives of the study are to assess the PD, PK, and immunological variables in the treatment course with rozanolixizumab and to assess whether long-term dosing of rozanolixizumab improves patient-reported outcomes (PROs). These include:

- The PD effect of rozanolixizumab as measured by the total immunoglobulin G (IgG) concentrations in serum
- The effects of rozanolixizumab on the concentrations of total protein, albumin, α - and β globulins, IgG subclasses, immunoglobulin M (IgM), immunoglobulin A (IgA), immunoglobulin E (IgE), and serum and plasma complement levels
- The incidence and emergence of anti-drug antibody (ADA) with respect to immunogenicity and PK and PD

- The effect of rozanolixizumab on complement and cytokines
- The plasma concentrations of rozanolixizumab administered by subcutaneous (sc) infusion
- The PD effect of rozanolixizumab as measured by neurofilament light chain (NF-L) in serum
- The effect of rozanolixizumab on CIDP-specific auto-antibody levels
- The effect of rozanolixizumab on vaccine antibody levels (influenza A and tetanus)
- The effect of rozanolixizumab on exploratory biomarkers, and explore the relationship between protein and metabolite biomarkers and cause, progression, and appropriate treatment of CIDP

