9.3.2 Anti-drug antibodies

Anti-rozanolixizumab antibodies will be measured using a three-tiered assay approach: screening assay, confirmatory assay and titration assay. The results for the ADA measurements will be listed by treatment group and timepoint based on the SS, including the Screening assay, confirmatory assay and titer (if applicable).

Samples will first be evaluated in the screening assay using a false positivity rate of 5% (reported as negative screen or positive screen), followed by analysis of screened positive samples in the confirmatory assay (which is a drug depletion assay) to confirm the true positivity of the samples (reported as negative immunodepletion or positive immunodepletion). Samples that are confirmed as positive will be evaluated in a titration assay to quantify the ADA level and will be reported as titer (reciprocal dilution factor including minimum required dilution (MRD)).

Screening, confirmatory and titer cut points of the respective assays will be determined by the bioanalytical laboratory.

The ADA status should be determined for each visit where samples were taken for ADA analysis:

- Sample values that are either negative screen or positive screen and negative immunodepletion will be defined as ADA negative
- Sample values that are positive screen and positive immunodepletion will be defined as ADA positive.

There will be six study participant classifications:

1. For study participants who are negative at baseline, and antibody negative at all sampling points post treatment (including FV)- pre ADA negative- treatment induced ADA negative

2. For study participants who are negative at baseline, and antibody positive at any sampling point post treatment (including FV)- pre ADA negative- treatment induced ADA positive. If a study participant has a missing pre-treatment sample (either missing or insufficient volume) at baseline with one or more ADA positive post-treatment samples will be also classified as pre ADA negative- treatment induced ADA positive
3. For study participants who are positive at baseline, and antibody negative at all sampling points post treatment (including FV)- pre ADA positive- treatment reduced ADA
4. For study participants who are positive at baseline, and are positive at any sampling point post treatment (including FV) with titer values of the same magnitude as baseline (i.e. \leq than a predefined fold difference from the baseline value)- pre ADA positive - treatment unaffected ADA

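### By-visit PK and IgG tables group participants by an ADA class that uses later samples, so those who convert during CIDP04 are filed as treatment-induced positive before any positive is confirmed

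*SAP*

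**What the plan says.** For concentration, SAP 9.1 plans: "Concentration data will be summarized for treatment rozanolixizumab by time point and ADA status (6 classifications". For total serum IgG and IgG subclasses, SAP 9.2.1 plans descriptive summaries "presented by treatment group and timepoint and ADA status (6 categories; see Section 9.3.2".

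SAP 9.3.2 defines ADA at two levels.

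- **Per visit:** "The ADA status should be determined for each visit where samples were taken for ADA analysis". Each sample is called negative or positive.
- **Per participant:** "There will be six study participant classifications". The second class is negative at Baseline and "antibody positive at any sampling point post treatment (including FV"). The fifth class, for participants positive at Baseline whose titer is boosted at any later sample, looks ahead in the same way.

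The per-visit status feeds the ADA counts and the listing. It is not named as the grouping for the concentration or IgG summaries. These analyses serve an exploratory objective: "The incidence and emergence of anti-drug antibody (ADA) with respect to immunogenicity and PK and PD".

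**The concern.** A by-visit table split by ADA should tell the reader whether concentration or IgG lowering differs between participants with and without antibody at that visit. The planned split does not do this, because the row is decided by samples taken later. Someone first confirmed positive at Week 61 counts in the treatment-induced positive row at Weeks 3, 7 and 13. A transient positive stays in that row after reverting.

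These are the only summary statistics in the SAP that relate ADA to concentration and IgG. If antibody lowers exposure or weakens IgG reduction only after it appears, mixing values from before and after conversion in one row shrinks the visible difference at early visits.

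**Working it through.** The documents give no ADA conversion rate, effect size or sample size for this analysis (the number of participants is redacted), so there is no figure of the plan's own to reproduce. The misfiling follows from the definitions alone. Its size needs assumptions.

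**Inputs from the documents**
- Post-Baseline ADA samples (Protocol Table 5-1 and Section 12): Weeks 3, 7, 13, 17, 21, 25, 37, 49, 61, 77 and 84, which is 11 on the full schedule.
- PK samples (Protocol Table 11-1): Visits 2, 4, 8, 14, 18 and 22, quarterly in Part 2, and Visit 26. Each has a scheduled ADA sample at the same visit.
- IgG is sampled at more visits than ADA (Protocol Table 5-1).
- ADA Baseline (SAP Table 3-1): CIDP01 Day 1 for previously treated participants, CIDP04 Day 1 for newly treated.

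**Assumptions**
- No ADA effect before the first confirmed positive, and a constant effect after it.
- True geometric mean ratio (GMR), positive versus never positive, of 0.50 for illustration.
- Three patterns of conversion timing, each spread evenly over the samples named.

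**Formula.** Let f be the share of the treatment-induced positive class already positive at a visit. On the log scale the class difference is f times the true difference, so

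observed GMR = (true GMR)^f.

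At Baseline f = 0 for everyone in this class who has a Baseline sample.

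**Results for a true GMR of 0.50**

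| Conversions spread evenly over | Week 3 | Week 7 | Week 13 | Week 25 |
|---|---|---|---|---|
| Weeks 3, 7, 13 | 0.5^(1/3) = 0.79 | 0.5^(2/3) = 0.63 | 0.5^1 = 0.50 | 0.50 |
| Six Part 1 samples, Weeks 3 to 25 | 0.5^(1/6) = 0.89 | 0.5^(2/6) = 0.79 | 0.5^(3/6) = 0.71 | 0.5^1 = 0.50 |
| All 11 samples, Weeks 3 to 84 | 0.5^(1/11) = 0.94 | 0.5^(2/11) = 0.88 | 0.5^(3/11) = 0.83 | 0.5^(6/11) = 0.69 |

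Timing alone therefore moves Week 7 from 0.63 to 0.88 and Week 13 from 0.50 to 0.83. The count of 11 assumes a Final Visit after Part 2. Protocol 8.4 schedules one, but a footnote to Table 5-1 says it should not be performed. With 10 samples, Week 7 is 0.5^(2/10) = 0.87 and Week 13 is 0.5^(3/10) = 0.81.

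**Other effect sizes.** With half the class converted (f = 0.5), a true GMR of 0.3 reads 0.55 and a true GMR of 0.7 reads 0.84. For IgG, summarised by arithmetic means, the observed difference is f times the true one: 20 percentage points read as 5, 10 and 15 at f = 0.25, 0.5 and 0.75.

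**Previously treated participants.** If a share p of the class is already positive on entry to CIDP04 and stays positive, and g is the share of the remainder converted by the visit, then f = p + (1 − p)g. As p rises, the observed GMR moves toward the true value. The documents do not give p.

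**Check by simulation.** For 200,000 participants with conversion spread over the six Part 1 samples, the class-based GMR was 0.89, 0.79 and 0.71 at Weeks 3, 7 and 13. Grouping by status at the visit gave about 0.50 each time.

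**The case against.** **Timing is kept elsewhere.** The ADA listing in SAP 9.3.2 sets each ADA result and titer beside the rozanolixizumab concentration and the time since dosing. Individual plots show concentration with titer, and titer with percentage change in IgG. Positivity by visit, first occurrence and cumulative prevalence are tabulated. This stands: the information is not lost, and the problem is confined to the by-visit summary tables.

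**The dilution could be small.** Conversion may be early, and previously treated participants who converted in CIDP01 and remain positive are correctly placed from entry. The 9.1 split pools both treatment groups. This also stands, and is why only a range is given. The direction is conditional too: if later converters already differ before the first confirmed positive, the bias could differ.

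**Fixed classes have a use.** Constant membership lets a reader follow one cohort over time, and the six classes keep reduced, unaffected and boosted antibody apart among Baseline-positive participants. This argues for adding a table rather than replacing the planned one.

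**Stronger readings a reader might infer**
- *A real ADA effect would look like no effect through most of Part 1.* Even with the latest timing pattern above, a halving reads 0.83 at Week 13 and 0.69 at Week 25. No between-class ratio is planned; the tables are descriptive.
- *The never-positive class is contaminated by early stoppers.* Someone negative at Weeks 3 and 7 who then stops contributes only visits at which the negative label is right.
- *The six-way split will empty the cells.* SAP 3.1 and 9.1 do suppress statistics in very small cells, but with the sample size redacted this cannot be shown.

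**Conclusion.** The point holds for the by-visit summaries in SAP 9.1 and 9.2.1. Participants who convert within CIDP04 appear in the treatment-induced positive row before any positive is confirmed; this needs no assumption. That the contrast is diluted rests on there being no ADA effect before conversion. The amount is not fixed by the documents: the Week 7 and Week 13 ranges in the table are illustrations for one assumed effect, and overstate the dilution to the extent that the class was already positive on entry.

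No primary or secondary result is touched. This is a cheap improvement to an exploratory, descriptive analysis, worth making because the stated objective concerns the emergence of ADA in relation to PK and PD.

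**What to change.** Keep the six-class tables. In SAP 9.1 and 9.2.1 add a summary at each time point by ADA status to date:

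1. Baseline negative, no confirmed positive to date;
2. Baseline negative, confirmed positive at or before the visit;
3. Baseline positive.

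Build it from the per-visit status already derived in 9.3.2. Each PK visit has its own scheduled ADA sample; at IgG visits without one, carry the latest earlier status forward and say so in a footnote. Add a note under the six-class tables that class membership uses all samples through the Final Visit.

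The cost is one derived by-visit variable and one extra table each for PK and IgG. The drawbacks are that group membership and n change over visits, transient positives remain in the positive-to-date row after reverting, and status is approximate at IgG visits between ADA samples, particularly in Part 2, where ADA is sampled every 12 weeks.
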